9.4 Continuous Toxicity Monitoring Rule

In addition to the safety lead-in, a continuous toxicity monitoring rule will be applied to this study to monitor for excessive or unexpected toxicity associated with study treatment (Ivanova *et al.*, 2005). Patients will be subjected to continuous toxicity monitoring during the first four cycles of study treatment. Sequential boundaries will be used to monitor the DLT rate. DLTs are defined in Section 9.2 above. According to this model, shown in the table below, enrollment will be halted if the number of DLTs is equal to or exceeds b_n out of n patients with completed DLT follow-up. This is a Pocock-type stopping boundary which yields a probability of crossing the boundary (early stopping) of at most 30% stopping when the rate of DLT is equal to the acceptable rate of 20% using a pre-defined sample size of 26 patients. This boundary is equivalent to testing the null hypothesis, after each patient, that the event rate is equal to 0.20, using a one-sided level 0.14 test.

With Amendment 5, the study was modified to substitute ASTX727 for SGI-110 (guadecitabine). The continuous toxicity monitoring rule will apply as defined above to patients treated with belinostat and ASTX727. Toxicities experienced by the initial cohort of 6 patients treated with SGI-110 (guadecitabine) and belinostat will not be considered in the model as it

applies to subsequent patients treated with ASTX727 and belinostat.

If the early stopping event occurs, the study will be halted and the investigators, CTEP, and the DSMB (if applicable) will discuss whether to close the study early for toxicity or modify the protocol to address the observed events. In addition, if any grade 5 event at least possibly related to study treatment occurs, the study will also be halted for review in this fashion.

Number of patients (n)	1	2	3	4	5	6	7	8	9	10	11	12	13
Boundary, b_n	-	2	2	3	3	3	4	4	4	4	5	5	5
Number of patients (n)	14	15	16	17	18	19	20	21	22	23	24	25	26
Boundary, b_n	5	6	6	6	6	7	7	7	7	8	8	8	8

Investigators are expected to report any DLT events directly to the study statistician and the Data Coordinating Center within 24 hours of their knowledge of such an event.

9.6 Analysis of Secondary Endpoints

9.6.1 Evaluation of Toxicity

Adverse event rates that are possibly, probably, or definitely related to treatment will be reported as counts and percentages per AE by grade and the number of patients with a given maximal grade of toxicity. We will also report the frequency and percentage of DLTs.

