1.2 Secondary Objectives

- 1.2.1 To evaluate the toxicity profile associated with belinostat and ASTX727.
- 1.2.2 To evaluate the progression free survival (PFS) associated with belinostat and ASTX727.
- 1.2.3 To evaluate the toxicity profile, objective response rate and progression free survival among the initial six patients treated with belinostat and SGI-110 (guadecitabine) prior to Amendment 5 in which ASTX727 was substituted for SGI-110 (guadecitabine).

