9.1.2 Secondary Endpoints

Secondary endpoints are the presence of treatment related AEs, the occurrence of DLTs, and PFS. Adverse events will be recorded at each clinical visit and will be categorized according to NCI CTCAE version 5.0. The attribution of AEs to each of the study drugs will also be recorded.

Secondary endpoints will be reported separately for the population of patients receiving belinostat and SGI-110 (guadecitabine) and the population of patients receiving belinostat and ASTX727.

The study will use a continuous toxicity monitoring rule as described in Section 9.4. DLTs are defined in Section 9.2 and to qualify as DLT must be attributed to the study drugs and not to disease, and occur (or first become evident) during the first four cycles of treatment for the purposes of continuous toxicity monitoring.

PFS is defined as the time from first treatment with the study drug to the earliest of either disease progression or death from any cause. Patients who are alive and progression free will be censored at the time of their last follow-up.

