9.2 Dose-Limiting Toxicity

The following definitions of dose-limiting toxicity (DLT) apply to both the safety lead-in (Section 9.3) and the continuous toxicity monitoring rule (Section 9.4). DLTs are defined as the following toxicities which are attributed to the study drug(s) and not to disease, and which occur (or first become evident) during a prespecified timeframe. For the purposes of the safety lead-in, this timeframe is the first two cycles of treatment. For the purposes of the continuous toxicity monitoring rule, this timeframe is the first four cycles of treatment.

1. Any grade ≥ 3 non-hematologic toxicity, except grade ≥ 3 fatigue, nausea, or vomiting which must persist > 5 days despite maximal supportive care to be considered dose limiting.
2. Any grade ≥ 4 hematologic toxicity lasting > 14 days, except grade 4 lymphopenia, which is not considered a DLT.
3. Grade ≥ 3 neutropenia with fever
4. Grade ≥ 3 thrombocytopenia with clinically significant bleeding
5. Any laboratory abnormality not otherwise addressed above which is associated with clinical sequelae and which fails to resolve to grade ≤ 1 within 5 days of occurrence, or any laboratory criteria meeting Hey's law for liver toxicity.
6. Any event leading to dose reduction or permanent discontinuation of any study drug during cycles 1-2 (applies to safety lead-in subjects only).

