10.2 Adverse Event Characteristics

- **CTCAE term (AE description) and grade:** The descriptions and grading scales found in the revised NCI Common Terminology Criteria for Adverse Events (CTCAE) version 5.0 will be utilized for AE reporting. All appropriate treatment areas should have access to a copy of the CTCAE version 5.0. A copy of the CTCAE version 5.0 can be downloaded from the CTEP website

http://ctep.cancer.gov/protocolDevelopment/electronic_applications/ctc.htm

- **For expedited reporting purposes only:**
 - AEs for the agent that are ***bold and italicized*** in the CAEPR (*i.e.*, those listed in the SPEER column, Section 10.1) should be reported through CTEP-AERS only if the grade is above the grade provided in the SPEER.
- **Attribution** of the AE:
 - Definite – The AE is *clearly related* to the study treatment.
 - Probable – The AE is *likely related* to the study treatment.
 - Possible – The AE *may be related* to the study treatment.
 - Unlikely – The AE is *doubtfully related* to the study treatment.
 - Unrelated – The AE is *clearly NOT related* to the study treatment.

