10.3 Expedited Adverse Event Reporting

10.3.1 Rave-CTEP-AERS Integration

The Cancer Therapy Evaluation Program Adverse Event Reporting System (CTEP-AERS) integration enables evaluation of post-baseline AEs entered in Rave to determine whether they require expedited reporting, and facilitates entry in CTEP-AERS for those AEs requiring expedited reporting.

All AEs that occur after baseline are collected in Medidata Rave using the Adverse Event form, which is available for entry at each treatment or reporting period, and used to collect AEs that start during the period or persist from the previous reporting period. The Clinical Research Associate (CRA) will enter AEs that occur prior to the start of treatment on a baseline form that is not included in the Rave-CTEP-AERS integration. AEs that occur prior to enrollment must begin and end on the baseline Adverse Event form and should not be included on the standard Adverse Events form that is available at treatment unless there has been an increase in grade.

Prior to sending AEs through the rules evaluation process, site staff should verify the following on the Adverse Event form in Rave:

- The reporting period (course/cycle) is correct, and
- AEs are recorded and complete (no missing fields) and the form is query-free (fields added to the form during study build do not need to be query-free for the integration call with CTEP-AERS to be a success).

The CRA reports AEs in Rave at the time the Investigator learns of the event. If the CRA modifies an AE, it must be re-submitted for rules evaluation.

Upon completion of AE entry in Medidata Rave, the CRA submits the AE for rules evaluation by completing the Expedited Reporting Evaluation form. Both NCI and

protocol-specific reporting rules evaluate the AEs submitted for expedited reporting. A report is initiated in CTEP-AERS using information entered in Medidata Rave for AEs that meet reporting requirements. The CRA completes the report by accessing CTEP-AERS via a direct link on the Medidata Rave Expedited Reporting Evaluation form.

In the rare occurrence that Internet connectivity is lost, a 24-hour notification is to be made to CTEP by telephone at [contact]. Once Internet connectivity is restored, the 24-hour notification that was phoned in must be entered immediately into CTEP-AERS using the deep link from Medidata Rave.

Additional information about the CTEP-AERS integration is available on the CTSU website:

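### The toxicity analysis reports only events attributed to treatment; an all-cause adverse-event table should stand beside it

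*Combined protocol and SAP*

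**What the plan says.** All references are to the combined protocol and SAP.

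- **Objective (1.2.1):** "To evaluate the toxicity profile associated with belinostat and ASTX727". It contains no restriction to attributed events.
- **Endpoint (9.1.2):** "Secondary endpoints are the presence of treatment related AEs, the occurrence of DLTs, and PFS". The same section requires separate reporting for the SGI-110 and ASTX727 groups and adds: "The attribution of AEs to each of the study drugs will also be recorded".
- **Analysis (9.6.1):** "Adverse event rates that are possibly, probably, or definitely related to treatment will be reported as counts and percentages per AE by grade". The sentence goes on to count patients by their maximal grade, without saying whether that count is also limited to related events. It is followed by: "We will also report the frequency and percentage of DLTs".
- **DLT definition (9.2):** DLTs are "toxicities which are attributed to the study drug(s) and not to disease", so they carry the same filter.
- **Data collection (10.3.1):** "All AEs that occur after baseline are collected in Medidata Rave using the Adverse Event form". Section 10.4 likewise requires every adverse event to be entered in routine submissions.

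The trial is single-arm (section 9), and section 6.1 states that ASTX727 had not been studied with an HDAC inhibitor.

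**The concern.** Under 9.6.1 as written, an event judged unlikely to be related, or unrelated, appears in no planned safety output. Attribution is a site-level judgement. In a randomised trial it can be checked against the event rate in the control arm; here there is no control arm, and the exact pair of drugs has no earlier clinical record to lean on. The protocol's own risk lists (10.1.1) warn that a combination may produce events not seen with either agent alone, which are the events on which attribution is hardest.

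At stake is how well the reported result answers objective 1.2.1. A reader of the final report would see rates already filtered by judgement and could not recover the unfiltered ones.

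**Working it through.** **1. The plan's own figure.** Section 9.6.1 states none. The nearest toxicity figure is in 9.4: at most a 30% chance of crossing the DLT boundary when the DLT rate is 20% and n = 26. An exact binomial recursion with the printed boundary gives 0.293, so that figure reproduces. It is not in dispute here.

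**2. Against all-cause incidence.** Let N = 26 (9.5, ASTX727 group), p = all-cause incidence of an event, s = share of affected patients whose event is attributed. Expected patients shown = N × p × s. The documents give neither p nor s for this trial; the values below are assumptions.

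| p | All-cause, N × p | s | Shown, N × p × s | Missing |
|---|---|---|---|---|
| 0.30 | 7.8 | 0.80 | 6.2 | 1.6 |
| 0.30 | 7.8 | 0.60 | 4.7 | 3.1 |
| 0.40 | 10.4 | 0.90 | 9.4 | 1.0 |
| 0.40 | 10.4 | 0.80 | 8.3 | 2.1 |
| 0.40 | 10.4 | 0.70 | 7.3 | 3.1 |
| 0.40 | 10.4 | 0.60 | 6.2 | 4.2 |

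Since s cannot exceed 1, the related-only count is never above the all-cause count and equals it only if every event is attributed. An all-cause table shows 7.8 or 10.4 whatever the value of s.

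**3. A pair of figures in the protocol.** Section 2.2.2.2 gives both kinds of rate for serious events with SGI-110 in 1,235 AML/MDS subjects: 966 with any serious event (966/1,235 = 78.2%) and 327 with a related one (327/1,235 = 26.5%). The ratio is 327/966 = 33.9%. That population has heavy background illness, and these are serious events on a different agent, so the ratio must not be carried over to chondrosarcoma. It shows only that the two summaries can differ widely.

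**4. Against the truly drug-caused rate.** Let d = drug-caused rate, g = background rate, se = share of drug-caused events attributed, fp = share of background events attributed, with the two sources independent within a patient. Reported rate = 1 − (1 − d × se)(1 − g × fp). All inputs are assumptions.

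| d | g | se | fp | Reported rate | Reported − d |
|---|---|---|---|---|---|
| 0.30 | 0.10 | 0.8 | 0.1 | 1 − 0.76 × 0.99 = 0.248 | −0.052 |
| 0.20 | 0.20 | 0.8 | 0.5 | 1 − 0.84 × 0.90 = 0.244 | +0.044 |
| 0.10 | 0.30 | 0.8 | 0.3 | 1 − 0.92 × 0.91 = 0.163 | +0.063 |

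The sign changes with the inputs, and nothing in the documents fixes them.

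**The case against.** The strongest reply is that the analysis matches its endpoint: 9.1.2 names treatment-related events and 9.6.1 tabulates them. That stands. The plan does not contradict itself, and amending 9.6.1 alone would create a mismatch.

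A reader might infer that the reported profile is simply biased low. The documents do not support that without qualification. Section 10.2 sets a low bar for a possible relationship, that the event "may be related", so background events can be counted in as well as drug-caused ones left out. Nor is attribution made blind: the risk lists rest on 757, 702 and 583 patients for SGI-110, ASTX727 and belinostat, and section 6.1 cites experience with related drug pairs.

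A reader might also infer that toxicity could go undetected. It would not be lost to oversight. Section 10.3.3 requires serious events to be reported to the sponsor whatever their cause, subject to the listed exceptions, and requires deaths within 30 days of the last dose to be reported regardless of causality. The gap is in planned reporting only.

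Nor does it follow that comparison with other series fails. Most adverse-event rates cited in sections 2.2.1.2, 2.2.2.2 and 2.2.3.2 are for related events, so the planned table is the like-for-like comparator for them and should be kept.

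Finally, maximal-grade counts and per-regimen reporting are already planned. What is missing is the all-cause table.

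**Conclusion.** The point holds as a gap in planned reporting. The only adverse-event outputs named are filtered by attribution, so they understate all-cause incidence unless every event is attributed. They also depend on a judgement that this design cannot check. The direction of error against truly drug-caused toxicity is unknown, which is itself a reason to show both tables.

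The size cannot be fixed from the documents. The 2 to 3 patients out of about 8 is illustrative and rests on an assumed 30% incidence and an assumed 20–40% judged unrelated. Those patients should not be read as misclassified drug toxicities; nothing shows that they are. The primary analysis and the stopping rules are unaffected.

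**What to change.** - **9.6.1:** add a table of all treatment-emergent adverse events regardless of attribution, counting each patient once per event at the maximal grade. Keep the planned related-event table beside it, and state for the maximal-grade count which set of events it covers.
- **9.1.2:** widen the safety endpoint to adverse events of any attribution, with treatment-related events as a named subset, so that endpoint and analysis agree.
- **Groups:** present both tables separately for the SGI-110 and ASTX727 regimens, as 9.1.2 already requires.
- **Definition:** state what counts as treatment-emergent. The rule in 10.3.1, under which pre-existing events move to the on-treatment form only if their grade increases, is a ready basis.

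The cost is a short wording change in two sections and one extra table from data already collected. Sample size, alpha, power and stopping rules stay as they are.

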9.6.2 Evaluation of Response

PFS is defined as the time from first treatment with the study drug to the earliest of either disease progression or death from any cause. Patients who are alive and progression-free will be censored at the time of their last follow-up. The Kaplan-Meier method will be used to evaluate time to event endpoints. Median PFS will be reported with a 95% confidence interval. Data will be presented as Kaplan Meier plots.

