6.3 Duration of Therapy

In the absence of treatment delays due to AEs, treatment may continue until one of the following criteria applies:

- Disease progression as defined by RECIST 1.1 criteria
- Intercurrent illness that prevents further administration of treatment
- Unacceptable AEs
- Patient decides to withdraw from the study
- General or specific changes in the patient's condition render the patient unacceptable for further treatment in the judgment of the investigator
- Clinical progression
- Patient non-compliance
- Pregnancy
 - All women of child-bearing potential should be instructed to contact the investigator immediately if they suspect they might be pregnant (e.g., missed or late menstrual period) at any time during study participation.
 - The investigator must immediately notify CTEP in the event of a confirmed pregnancy in a patient participating in the study.
- Termination of the study by sponsor
- The drug manufacturer can no longer provide the study agent

The reason(s) for protocol therapy discontinuation, the reason(s) for study removal, and the corresponding dates must be documented in the Case Report Form (CRF).

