6.4 Duration of Follow-Up

Patients will be followed for up to 24 months after removal from study or until death, whichever occurs first. During the follow-up period, patients will be evaluated in the clinic or contacted by telephone approximately once every 3 months to ascertain information related to disease status and subsequent anti-cancer treatment. Patients removed from study for unacceptable AEs will be followed until resolution or stabilization of the AE.

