7.4 Dose Modifications for Hematologic Toxicity

Both study agents are associated with myelosuppression. In order to begin a new treatment cycle, criteria specified in Section 7.3 must be met. A delay of up to 4 weeks is permitted to allow toxicity to resolve and initiate a new cycle of treatment. If counts have not recovered despite a 4 week delay from the scheduled start date, the patient should be discontinued from the study. Because the agents are administered concurrently, it may be difficult to attribute hematologic toxicity to one of the two agents with certainty. In general, SGI-110 (guadecitabine) or ASTX727 (whichever agent the patient is receiving) is associated with more frequent myelosuppression than belinostat. Therefore, a stepwise approach to dose modification is recommended, beginning with SGI-110 (guadecitabine) or ASTX727, as shown in the table below. If the investigator believes a hematologic toxicity is clearly attributable to one of the two drugs, that drug may be preferentially modified.

Observed Hematologic Toxicity (at any time during cycle)	Recommended Management
ANC <500/ μ L Hemoglobin <7 g/dL Platelets <25,000/ μ L	Delay cycle. Monitor complete blood count at least weekly. Transfuse and/or use growth factor per institutional guidelines. When criteria for a new cycle are met, resume at one dose level lower , per the table immediately below.
Grade 3 or 4 neutropenic fever	
Grade 3 thrombocytopenia with bleeding	

Other hematologic AEs deemed clinically significant and for which dose modification is deemed necessary by the treating investigator.	
ANC 500-999/ μ L Hemoglobin 7.0-7.9 g/dL Platelets 25,000-74,999/ μ L	
Delay cycle. Monitor complete blood count at least weekly. Transfuse and/or use growth factor per institutional guidelines. When criteria for a new cycle are met, resume at the same dose if the delay was 14 days or less, otherwise resume at one dose level lower, per the table immediately below.
 
If hematologic toxicity requiring a dose reduction occurs, and a delay is also needed, only one dose reduction is applied.

Hematologic Toxicity Event	Recommended Management
First Event	Reduce SGI-110 (guadecitabine) or ASTX727 by one dose level
Second Event	Reduce belinostat by one dose level
Third Event	Reduce SGI-110 (guadecitabine) or ASTX727 by one dose level
Fourth Event	Reduce belinostat by one dose level

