F	Coagulation factors include: aPTT, INR; required pre-study and as clinically indicated. Local laboratory testing is permitted.													
G	Serum or urine pregnancy test (for women of childbearing potential) must be completed at screening. If results are positive, the patient is ineligible and must be discontinued from the study.													
H	A 12-lead ECG is performed at screening and end of study. Additional ECGs are performed as clinically indicated.													
I	MRI or CT imaging to evaluate disease status is performed at baseline and once every 2 cycles (8 weeks) \pm 5 days. Imaging should be performed prior to the initiation of the next cycle of study treatment whenever possible.													
J	Pre-treatment biopsy is performed within 21 days of C1D1. The pre-treatment biopsy may only be collected after informed consent is obtained. On-study biopsy is performed on Day 3, 4, or 5 of cycle 2, 2-8 hours post-treatment with the study agents whenever possible. If the start of C2 is delayed, the biopsy should be delayed accordingly. The on-study biopsy should not be obtained if the patient has not begun dosing for C2.													
K	Blood collection for germline whole exome sequencing. Pre-treatment collection is performed within 21 days of C1D1. The pre-treatment research blood collection may only be collected after informed consent is obtained.													
L	All screening assessments must be performed within 21 days of C1D1.													
M	All assessments occur on day 1 of the specified week, unless otherwise noted. Start of cycle laboratory assessments may be performed up to 3 days prior to initiating treatment for a new cycle. Between cycle laboratory assessments may be performed \pm 3 days from the scheduled date. Local laboratory testing is permitted.													
N	Off-study evaluations must be performed within 21 days of the last dose of the study drug.													

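### PFS is censored at last follow-up, which can be a telephone contact long after the last scheduled scan, so the tail of the Kaplan-Meier curve reads high to the extent that off-treatment progression is missed

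*Combined protocol and SAP*

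**What the plan says.** The event is disease progression or death from any cause, counted from first treatment (9.1.2, 9.6.2). On censoring, 9.6.2 says "Patients who are alive and progression-free will be censored at the time of their last follow-up" and 9.1.2 says "Patients who are alive and progression free will be censored at the time of their last follow-up". Section 12.1.6 defines PFS again without a censoring rule. No section ties censoring to a tumour assessment.

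On follow-up, 6.4 says "Patients will be followed for up to 24 months after removal from study or until death, whichever occurs first", and that "patients will be evaluated in the clinic or contacted by telephone approximately once every 3 months to ascertain information related to disease status". It does not require imaging at these contacts. The calendar (Section 11, footnote I) schedules imaging at baseline and every two cycles, that is every 8 weeks, and marks imaging once more in the off-study column. Footnote N sets the timing of that visit: "Off-study evaluations must be performed within 21 days of the last dose of the study drug". No scan is scheduled after it.

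Stopping without RECIST progression is foreseen. Section 6.3 lists unacceptable adverse events, intercurrent illness, non-compliance and loss of drug supply, among other reasons. Section 7.4 adds "If counts have not recovered despite a 4 week delay from the scheduled start date, the patient should be discontinued from the study".

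**The concern.** The censoring date and the assessment schedule do not match. A patient who comes off treatment without progression has one more scheduled scan and then contacts about every 3 months. If a contact records no progression, the whole interval back to the last scan enters the risk set as progression-free time. If the tumour has grown in that interval and nobody has imaged it, the patient stays in the denominator when an event should have been counted, and the curve sits too high.

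PFS is a stated secondary objective for the ASTX727 patients (1.2.2) and for the six SGI-110 patients (1.2.3). Section 9.6.2 promises a median with a 95% confidence interval and Kaplan-Meier plots. In a single-arm trial in a rare disease, readers are likely to set those plots beside other series. The protocol is stricter for duration of response, which 12.1.5 ends at objectively documented progression.

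**Working it through.** **1. The gap.** 24 months is 104 weeks, and 104 / 8 = 13 scan intervals. This is approximate, because the 24 months run from removal from study and not from the last scan.

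**2. Plan figure.** There is none to reproduce: the documents give no PFS target, event count or power.

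**3. Inputs.** From the documents: n = 26, scans every 8 weeks on treatment, a scan at leaving, contacts every 3 months, 24 months of follow-up. Assumed, because the documents give no values: exponential progression with median 4 months; 10%, 20% or 30% leaving without progression for reasons unrelated to prognosis; median 12 months from progression to death; all, half or none of off-treatment progression captured at contacts.

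**4. Reference curve.** This is the rate seen if everyone were scanned every 8 weeks until the event. Eight weeks is 56 / 30.4375 = 1.84 months. The last scans before 6 and 12 months fall at 3 × 1.84 = 5.52 and 6 × 1.84 = 11.04 months.
- 6 months: 0.5^(5.52/4) = 0.384 (latent: 0.5^(6/4) = 0.354)
- 12 months: 0.5^(11.04/4) = 0.148 (latent: 0.5^(12/4) = 0.125)

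The simulated references (0.379-0.386 and 0.146-0.150) agree.

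**5. Simulation, 3,000 trials per setting.** Entries are reference / current rule / censoring at the last scan with recorded progressions kept as events.

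| Time, capture | 10% leave | 20% leave | 30% leave |
|---|---|---|---|
| 12 months, all | 0.146 / 0.148 / 0.147 | 0.150 / 0.156 / 0.154 | 0.147 / 0.157 / 0.154 |
| 12 months, half | 0.146 / 0.169 / 0.156 | 0.146 / 0.195 / 0.171 | 0.147 / 0.223 / 0.185 |
| 12 months, none | 0.147 / 0.189 / 0.166 | 0.146 / 0.235 / 0.191 | 0.147 / 0.286 / 0.219 |
| 6 months, all | 0.379 / 0.387 / 0.386 | 0.386 / 0.404 / 0.403 | 0.384 / 0.413 / 0.411 |
| 6 months, half | 0.381 / 0.397 / 0.391 | 0.386 / 0.420 / 0.407 | 0.381 / 0.436 / 0.415 |
| 6 months, none | 0.382 / 0.405 / 0.393 | 0.382 / 0.431 / 0.407 | 0.382 / 0.462 / 0.425 |

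Current rule minus reference at 12 months: 0.2 to 1.0 points (all), 2.3 to 7.6 (half), 4.2 to 13.9 (none). At 6 months: 0.8 to 2.9, 1.6 to 5.5 and 2.3 to 8.0.

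**6. Share removed by moving the date.** At 12 months, 30% leaving, no capture: (0.286 − 0.219) / (0.286 − 0.147) = 0.067 / 0.139, about 48%. At 6 months, 30% leaving, half capture: (0.436 − 0.415) / (0.436 − 0.381) = 0.021 / 0.055, about 38%. With full capture almost nothing is gained.

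**7. Median.** The mean estimated median is 4.7-4.8 months in the reference. The current rule raises it by 0.03-0.13 months (all captured), 0.10-0.44 (half) and 0.17-0.84 (none). Moving the date changes those to 0.03-0.13, 0.10-0.37 and 0.15-0.57.

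**8. Other assumptions.** A separate large-sample run used latent medians of 4, 6 and 8 months and 15%, 30% and 45% leaving. Missing every off-treatment progression raised the 12-month rate, over complete ascertainment, by 0.415 − 0.388 = 2.7 points at the least (8 months, 15%) and 0.370 − 0.164 = 20.6 points at the most (4 months, 45%). The median was unchanged in five of the nine settings. In the other four it rose by 1.8 to 3.0 months; these were all three 45% settings, and 30% leaving with a median of 8 months.

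**9. Scale.** The standard error of a 38% rate with 26 patients is √(0.38 × 0.62 / 26) = 0.095, or 9.5 points.

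**The case against.** The contacts in 6.4 exist to learn disease status. Section 12.1 asks for re-evaluation every 8 weeks without limiting this to treatment. Section 12.1.4.3 asks for every effort to document progression after treatment stops for a decline in health. A reader might infer from the censoring rule that patients are credited with two years of wholly unassessed time. The documents do not support that: the time is un-imaged, not unassessed, and any progression recorded at a contact is an event. This stands, and it makes the no-capture row an upper bound. It does not settle the point, because none of these passages sets a censoring date or schedules a scan.

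Withdrawal is also a poor example. Section 6.3 lists "Patient decides to withdraw from the study", but someone who leaves the study altogether may have no later contact, so last follow-up would fall close to the last scan. The patients who matter are those who stop treatment and stay in follow-up.

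Finally, 9.6.2 promises a median and plots, not 6- or 12-month rates, and every size above rests on assumed rates. Both are correct. The 6- and 12-month figures describe the height of the plotted curve, and the one promised number usually moves little.

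**Conclusion.** The point holds in limited form. The rule as written biases the PFS curve upward whenever progression after treatment is missed, and nothing else in the documents corrects the censoring date. The size cannot be derived from the documents. Under the assumptions in step 3 the inflation at 12 months runs from about 1 point or less to 14 points, depending almost wholly on capture. Partial capture is the likeliest reading of the follow-up text.

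Two stronger readings should be resisted. A reader might infer that the reported median will be badly wrong; with a 4-month latent median and 10-30% leaving it shifts by less than a month on average, and the larger shifts in step 8 need both heavy leaving or longer PFS and every progression missed. A reader might also infer that the go/no-go decision is compromised. It is not: 9.1.1 decides on response counts, and PFS is a descriptive secondary endpoint with no hypothesis or threshold. The correction is worth making because it is cheap, but the trial's main conclusion does not depend on it.

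**What to change.** Leave the event definition unchanged: disease progression or death from any cause, including progression recorded off treatment at a follow-up contact. In 9.1.2 and 9.6.2 change only the censoring sentence, to: *Patients who are alive with no progression recorded are censored at the date of their last evaluable tumour assessment (date of first treatment if none).*

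Do not limit the event to documented RECIST 1.1 progression. That would censor patients whose progression is known only clinically or by telephone. In simulation at 30% leaving it gave a 12-month rate of 0.219-0.222 at every capture level, against a reference of about 0.147. The current rule gives about 0.157 with full capture and 0.222 with half, so the restriction would be worse in the first case and no better in the second.

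Keep last-contact censoring as one sensitivity analysis. Report how many patients stopped treatment without documented progression, and how many events were recorded without imaging.

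The cost is wording in two sections; scan dates and disease status are already collected. PFS may come out slightly shorter with a wider interval. If capture is complete the new rule can read slightly low, by about 1 point or less at 12 months in these simulations (up to 0.7 points with a latent median of 8 months). Some upward bias remains if leaving is related to prognosis, or if a patient dies with progression never recorded and so counts as an event only at death.
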